- The lower limit of the two-sided standardized asymptotic 95% CI on the difference between groups (HRV Liq group minus HRV Lyo group) in the percentages of subjects with concentration of antibodies against anti-PRP $\geq 1.0 \mu\text{g/mL}$ is $\geq 10\%$ (clinical limit for non-inferiority).

- To rule out a 10% decrease in seroresponse to PT, FHA and PRN antigen when *Pediarix* is co-administered with PCV-free-liquid HRV vaccine compared to when *Pediarix* is co-administered with the currently licensed lyophilized HRV vaccine.
 - seroresponse is defined as the percentage of subjects showing an antibody concentration above a threshold that leads to 95% seroresponse in the control group (lyophilized HRV vaccine),
 - p-value on the difference in seroresponse between groups is $<2.5\%$ for each PT, FHA and PRN antigen (p-value is computed by integrating on the p-value for the null hypothesis that the seroresponse rate in the liquid group is $<85\%$ and the a-posteriori probability of the threshold in the lyophilized group).

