6. STATISTICAL ANALYSES

Note that standard data derivation rule and stat methods are described in annex 1 and will not be repeated below.

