6.3.1.2. Between group assessment

For each treatment group, one month after Dose 3 of routine infant vaccines at Visit 4 (Month 5) time-point:

- Two-sided asymptotic standardized 95% CIs for the difference in the percentage of subjects with titer/concentration above or equal to pre-specified clinical thresholds will be computed (HRV Liq group minus HRV Lyo group).
- The two-sided 95% CIs for the group GMC/GMT ratio (HRV Liq group over HRV Lyo group) will be computed using an ANOVA model on the logarithm10 transformation of the concentrations. The ANOVA model will include the vaccine group as fixed effects. In addition, for anti-HBs, the model will include the Hepatitis B vaccination history as co-variable.
- For the group comparison in anti-PT, FHA, PRN seroresponse at one month post dose 3, P-value for testing $H_0: P \leq 85\%$ vs. $H_1: P > 85\%$ ($P = \%$ of subjects in HRV liq group with seroresponse (above a threshold that leads to 95% seroresponse in the HRV lyo group) will be computed. P-value will be computed by integrating on the p-value for the null hypothesis that the seroresponse rate in the HRV lyo group is $< 85\%$ and the a-posteriori probability of the threshold in the HRV liq group.

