6.3.1.3. Statistical methods

- The exact 95% CIs for a proportion within a group will be based on the method by Clopper [see section 11.1].
- The standardized asymptotic CI for the group difference in proportion is the method 6 described in the Newcombe paper [see section 11.1]
- The 95% CIs of the group GMC/GMT ratios will be computed using an ANOVA model on the logarithm10 transformation of the concentrations/titers. The ANOVA model will include the vaccine group as fixed effects. In addition, for anti-HBs, the model will include the Hepatitis B vaccination history as co-variable.
- The 95% CI for GMTs/GMCs will be obtained within each group separately. The 95% CI for the mean of log-transformed titer/concentration will be first obtained assuming that log-transformed values were normally distributed with unknown

variance. The 95% CI for the GMTs/GMCs will then be obtained by exponential-transformation of the 95% CI for the mean of log-transformed titer/concentration.

- P-value for seroresponse endpoint will be computed by integrating on the p-value for the null hypothesis that the seroresponse rate in the HRV lyo group is <85% and the a-posteriori probability of the threshold in the HRV liq group.

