7.1. Control on type I error

A 2.5% nominal type I error will be used for each co-primary evaluation. To control the type I error below 2.5%, a hierarchical procedure will be used for the multiple study objectives. That is, an objective will be reached if its associated criterion is met and the previous objectives were reached. The same order in which the study objectives are listed in Section 3.1 will be considered for hypothesis testing.

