9. CHANGES FROM PLANNED ANALYSES

The planned analysis of the percentage of doses and of subjects reporting at least one grade 3 causally related symptom (solicited or unsolicited) during the 8 day (Day 1-Day 8) solicited follow-up period post-vaccination will not be generated considering this analysis is of limited clinical relevance and is not part of the standard analyses planned in other PCV free Rota studies.

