11.1.1. Pertussis vaccine response analysis

Usually immunological titres above t^* , a fixed cut-off, are used as surrogate of efficacy. Therefore, non-inferiority of a new vaccine is claimed when $P(t^*)$, the proportion of subjects with post-vaccination titres above t^* , is not decreased as compared to a control vaccine by more than Δ , a pre-specified non-inferiority margin.

For pertussis non-inferiority on seroresponse,

let $P_i(t^*)$ be the percentage of subjects with titer above t^* in group i, i=1 for Liquid and i=0 for lyo), the null hypothesis can be written as,

$$H_0: P_1(t^*) < 85\% = 95\% - \Delta$$

with t^* calibrated so that $P_0(t^*) = 95\%$

Would t^* be fixed, the p-value would be computed from a binomial distribution with probability=85%, N=number of subjects in group Liquid and n=the number subjects with titer above t^* .

As t^* is random, the expected p-value can be computed accounting for the distribution of t^* as $\int \Pr\{ \text{Bin}(n_1, \tau - \Delta) > n_1 P_I(t^*) \} f_0(t^*) dt^*$

with $f_0(t^*)$ denoting the distribution of t^* .

Based on the hypothesis testing principle that the type I error is the expected percentage of falsely rejecting H_0 when H_0 is true, the proposed test is to reject H_0 when the expected p-value is below the type I error.

The distribution of $f_0(t^*)$ will be estimated using a non-parametric bootstrapping (1000 repetitions) approach.

The operating characteristics of the method was assessed via simulations. The log-transformed antibody titre of a subject in study group i was obtained from a normally distributed random function with mean and variance (μ_i, σ^2_i) ($i=0$ for the control group).

To simulate data under the condition that $P_I(t^*) = \tau - \Delta_A$, the values of μ_0, σ_0, μ_I , and σ_I were constraint so that $\mu_0 + \sigma_0 Z_\tau = \mu_I + \sigma_I Z_{\tau - \Delta_A}$ with Z_τ denoting the Probit function.

Simulations were done under 2 conditions:

- The null hypothesis that $P_I(t^*) = \tau - \Delta$: This allowed estimating the true type I error rate of tests supposed to control the type I error below 2.5%. This was estimated by the proportion of simulations for which the p-value rejected $H_0: P_I(t^*) < \tau - \Delta$ at significance level 2.5%

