- The alternative hypothesis that $P_I(t^*) = \tau - \Delta_A$: This allowed estimating the power of the tests. This was estimated by the proportion of simulations for which the p-value rejected $H_0: P_I(t^*) < \tau - \Delta$ at significance level 2.5%

The simulation also included power and type I estimation when using Miettinen non-inferiority p-value with 10% margin. The simulation indicated that the proposed stat method controlled well the type I error.

Table 6 Power for a non-inferiority margin $\Delta = 10\%$, $P_0(t^*) = 95\%$ and a 2.5% significance level

μ_0	$\sigma_0 = \sigma_1$	n_0	μ_1	n_1	$P_1(t^*)$	P_{vals}	P_{val_n}
Impact of n_0							
0	1	100	0	300	95%	94.2%	77.9%
0	1	150	0	300	95%	96.3%	89.7%
0	1	300	0	300	95%	99.4%	98.1%
Impact of σ_0							
0	1	300	0	300	95%	99.4%	98.1%
0	10	300	0	300	95%	99.5%	98.6%
0	100	300	0	300	95%	99.4%	98.5%
Impact of true difference							
0	1	300	-.2	300	92.575%	90.9%	75.8%
0	1	300	-.3	300	91.066%	71.5%	45.1%
0	1	300	-.4	300	89.341%	47.8%	21.7%
Impact of n_1							
0	1	300	-.3	250	91.066%	68.8%	45.2%
0	1	300	-.3	200	91.066%	61.5%	40.8%
0	1	300	-.3	150	91.066%	53.4%	33.2%

 P_{vals} = Power for the traditional method (Miettinen, 1985). The method assumes that t^* is fixed P_{val_n} = Power for the proposed method**Table 7 Type I error for a non-inferiority margin $\Delta = 10\%$, $P_0(t_0) = 95\%$ and a 2.5% significance level**

μ_0	σ_0	n_0	μ_1	σ_1	n_1	$P_1(t^*)$	P_{vals}	P_{val_n}
0	1	300	-0.6084	1	300	85%	7.9%	0.8%
0	1	300	0	1.5870	300	85%	3.2%	0.9%
0	1	300	-0.2	1.3941	300	85%	3.1%	0.9%

 P_{vals} = type I error for the traditional (method Miettinen, 1985). The method assumes that t^* is fixed. P_{val_n} = type I error for the new method

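### Four analysis passages swap the two arms in the co-primary pertussis seroresponse test, against the objectives, the stated hypotheses and SAP Annex 11.1.1

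*SAP*

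**What the plan says.** The second co-primary objective (Protocol 2.1, SAP 3.1) is to rule out a 10% decrease in seroresponse to PT, FHA and PRN. The threshold is the concentration that gives 95% seroresponse in the lyophilized control group. The null is that the liquid group's rate is below 85%, and the p-value is averaged over "the a-posteriori probability of the threshold in the lyophilized group". It must be below 2.5% for each antigen.

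SAP Annex 11.1.1 gives the algorithm in the same direction. Group 1 is Liquid, group 0 is Lyo, the threshold is calibrated in Lyo, and for a fixed threshold the p-value is "computed from a binomial distribution with probability=85%, N=number of subjects in group Liquid". The threshold's distribution comes from 1000 bootstrap repetitions.

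SAP 6.3.1.3 and Protocol 10.9.1 describe the p-value as an integral over the p-value for the null that "the seroresponse rate in the HRV lyo group is <85% and the a-posteriori probability of the threshold in the HRV liq group". SAP 6.3.1.2 and Protocol 10.7.2 first state H0 and H1 with P defined in HRV Liq. The same bullet then closes with the swapped sentence, ending in "the a-posteriori probability of the threshold in the HRV liq group".

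SAP section 6 says that "stat methods are described in annex 1 and will not be repeated below".

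**The concern.** Both group names are exchanged, so the sentence describes a coherent but different test: whether the lyophilized vaccine is non-inferior to the liquid one. The worse the liquid group does, the more easily that test succeeds.

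This is the pass/fail rule of a confirmatory objective, and the documents state it in two opposite directions. SAP section 6 refers to the annex and says methods will not be repeated, yet 6.3.1.3 repeats this one, reversed and without H0/H1. No sentence sets an order of precedence. SAP section 9 does not mention the discrepancy; its only entry concerns "The planned analysis of the percentage of doses and of subjects reporting at least one grade 3 causally related symptom". If the direction were settled after results were known, the choice would be open to challenge.

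**Working it through.** **1. The passages side by side**

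| Place | Arm tested against 85% | Arm that sets the threshold |
|---|---|---|
| Protocol 2.1, SAP 3.1 | Liq | Lyo |
| H0/H1 in Protocol 10.7.2 and SAP 6.3.1.2 | Liq | Lyo |
| Protocol Table 18 footnote (definition of seroresponse) | Liq | Lyo |
| SAP Annex 11.1.1 | Liq | Lyo |
| p-value sentence, Protocol 10.7.2 and 10.9.1 | Lyo | Liq |
| p-value sentence, SAP 6.3.1.2 and 6.3.1.3 | Lyo | Liq |

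**2. Reproducing the plan's figures**

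The annex test was simulated with normal log titres. The threshold is the 5th percentile of the reference arm, weighted by its exact bootstrap distribution in place of 1000 resamples. The p-value is the weighted binomial tail at 85%, and H0 is rejected below 0.025. Each scenario had 6,000 to 10,000 trials. The ranges cover a strict and a non-strict binomial tail. The lyo SD is 1.

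| Scenario | Plan | Annex direction | Swapped |
|---|---|---|---|
| 416/416, equal arms (Table 18: type II error 0.1%) | 99.9% | 99.9–100.0% | 99.8–100.0% |
| 300/300, equal (SAP Table 6) | 98.1% | 98.1–98.6% | 97.8–98.4% |
| 300/300, liq mean −0.2 | 75.8% | 71.0–75.0% | 100% |
| 300/300, liq mean −0.3 | 45.1% | 42.6–47.6% | 100% |
| 300/300, liq mean −0.4 | 21.7% | 17.8–21.3% | 100% |
| 300/300, three nulls (SAP Table 7) | 0.8%, 0.9%, 0.9% | 0.8–1.4% | 100% |

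The annex match is approximate because the SAP does not state its percentile rule. The swapped form cannot produce the Table 6 rows with a true difference, or Table 7. The SAP's statement that "The simulation indicated that the proposed stat method controlled well the type I error" therefore applies only to the annex direction. Table 18 cannot tell the two apart: its footnote assumes identical distributions, and with equal group sizes the problem is symmetric.

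**3. Type I error at the planned 416 per group**

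In each Table 7 null the true liquid rate above the lyo 5th percentile is 85%. The swapped test looks at the lyo rate above the liquid 5th percentile:

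- Mean −0.6084: Φ(1.6449 + 0.6084) = 98.8%.
- SD × 1.587, equal mean: Φ(1.6449 × 1.587) = 99.5%.
- Mean −0.2, SD × 1.3941: Φ(0.2 + 1.6449 × 1.3941) = 99.4%.

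All three lie far above 85%. The swapped test passes 100% of trials in each; the annex test passes about 1.4% to 2.1%.

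**4. Does the first objective catch it?**

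Under SAP 7.1 "an objective will be reached if its associated criterion is met and the previous objectives were reached", so the lower 95% limit of the GMC ratio must first reach 0.67. With lyo SD σ from Table 18 (PT 0.297, FHA 0.293, PRN 0.409), liquid SD rσ and mean shift δ (in units of σ):

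SE = σ·√[(1 + r²)/416], and P(pass) = Φ[(δσ − log10 0.67)/SE − 1.963], with log10 0.67 = −0.1739.

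Example, PRN with δ = −0.2 and r = 1.3941: SE = 0.409 × √(2.9435/416) = 0.0344; (−0.0818 + 0.1739)/0.0344 − 1.963 = 0.715; P = 76%.

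| Liquid arm | PT | FHA | PRN |
|---|---|---|---|
| Mean −0.6084 SD | 1.1% | 1.5% | 0.0% |
| SD × 1.587, equal mean | 100% | 100% | 99.6% |
| Mean −0.2 SD, SD × 1.3941 | 99.6% | 99.7% | 76.3% |

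Because the swapped test passes every trial in these scenarios, the table also gives the share passing both criteria under the swapped wording. In the two wider-spread cases the annex direction passes both in about 1.4% to 2.1%. These shares are per antigen, not joint over all criteria.

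**5. A better liquid arm**

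With the liquid mean 0.3 SD higher, the swapped test passes about 65% to 69% of trials. At 0.6084 SD higher it passes 1.3% to 1.7%. The annex test passes 100% in both.

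**The case against.** The strongest reply is that the documents largely settle the matter. Every passage that defines the hypothesis or the algorithm has the arms the right way round, and in SAP 6.3.1.2 the swapped sentence contradicts its own bullet. SAP section 6 refers to Annex 1, and only Annex 11.1.1 can be programmed. SAP 6.3.1 repeats protocol text, so this looks like one slip carried forward. That stands: the plan as a whole does not prescribe the inverted test, and the harm depends on literal programming.

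The wider-spread cases are also stress tests. Protocol Table 17 shows SD ratios across its three groups of only 0.297/0.257 = 1.16 (PT), 0.293/0.255 = 1.15 (FHA) and 0.409/0.397 = 1.03 (PRN). With equal means, these give liquid rates of 92.3%, 92.4% and 94.5%, not 85%. That stands too, but these are the SAP's own null scenarios, and a criterion meant to detect a weak lower tail must work in them.

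Finally, the annex follows the protocol's objective and departs only from a mistaken sentence, so the missing entry in SAP section 9 is minor. That is fair. It remains true that SAP 6.3.1.3 and Protocol 10.9.1 carry no H0/H1 to correct them, and that nothing sets precedence.

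**Conclusion.** The concern holds. A confirmatory criterion is written in opposite directions, and four passages have the arms reversed. The intended test is recoverable, and the sample size and power figures are unaffected.

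If programmed as those passages read, the test would pass a liquid arm truly at 85% in 100% of trials instead of about 1.4% to 2.1%. It would also penalise a liquid arm that did better. The GMC criterion would block a pure shift but would let through 76% to 100% of trials per antigen in the two wider-spread nulls.

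These figures assume normal log titres, 416 evaluable per group, the Table 18 SDs for the lyo arm and literal use of the swapped wording. It must be corrected before analysis because it is a co-primary decision rule and the plan's stated power would not reveal the error.

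**What to change.** In SAP 6.3.1.2 and 6.3.1.3, exchange the two group names, for example: *The p-value averages the binomial p-value for H0 (seroresponse rate in HRV Liq ≤85%) over the distribution of the threshold estimated in HRV Lyo.* Add one sentence that Annex 11.1.1 governs. The ≤ sign matches the H0 already stated in 6.3.1.2; the objectives and annex write <, and one form should be used throughout.

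For Protocol 10.7.2 and 10.9.1, make the same exchange by amendment or record it as a correction in SAP section 9. If it is recorded in the SAP, mention it in the final report as well, since Protocol 10.10 asks for changes to the statistical plan to be described there.

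Do this before serology is analysed by group. The cost is two names in each passage, one sentence of precedence, and either a protocol amendment or one SAP entry. Sample size, alpha, data collection and method stay as they are.

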6.3.2. Additional considerations

Summaries will be generated by frequent race and by gender using PPS. Note that a race category is considered if it includes more than 40 subjects. Infrequent race categories will be combined together and summarized if it includes more than 40 subjects.

6.4. Analysis of safety

6.4.1. Analysis of safety planned in the protocol

The ES will be used for the analysis of safety.

The following calculations will be performed for each group:

The percentage of doses and of subjects reporting at least one symptom (solicited or unsolicited) during the 8 day (Day 1-Day 8) solicited follow-up period post-vaccination will be computed, along with exact 95% CI. The same calculations will be done for symptoms (solicited or unsolicited) rated as grade 3 in intensity, those assessed as causally related to vaccination, those rated as grade 3 in intensity with causal relationship to vaccination and those that resulted in a medically attended visit.

The percentage of doses and of subjects reporting each individual solicited general symptom will be computed, over the 8 day (Day 1-Day 8) solicited follow-up period post-vaccination, along with exact 95% CI. The same calculations will be done for each individual general solicited symptom rated as grade 3 in intensity, those assessed as causally related to vaccination, those rated as grade 3 in intensity with causal relationship to vaccination and those that resulted in a medically attended visit. For fever, additional analyses will be performed by 0.5°C increments. These calculations will also be performed by sex and race.

The verbatim reports of unsolicited AEs will be reviewed by a physician and the signs and symptoms will be coded according to MedDRA. Every verbatim term will be matched with the appropriate Preferred Term. The percentage of subjects with unsolicited AEs occurring within 31 day (Day 1-Day 31) follow-up period after any dose with its exact 95% CI will be tabulated by group, and by preferred term. Similar tabulation will be done for unsolicited AEs rated as grade 3, for unsolicited AEs with causal relationship to vaccination, for unsolicited AEs rated as grade 3 with causal relationship to vaccination and those that resulted in a medically attended visit.

The percentage of subjects who started taking at least one concomitant medication, antipyretic medication and prophylactic antipyretic medication during the 8 day (Days 1-8) and 31 day (Days 1-31) follow-up period post-vaccination will be tabulated by dose, overall per subject and over all the doses.

Subjects who experienced at least one SAE during the entire study period (from Dose 1 till ESFU Contact at Month 10) will be reported and the SAEs will be described in detail.

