6.4.2. Additional considerations

Safety analysis will be done per administered dose. Subjects who missed reporting symptoms (solicited/unsolicited or concomitant medications) will be treated as subjects without symptoms (solicited/unsolicited or concomitant medications, respectively). A sensitivity analysis will be performed on documented doses i.e. accounting only for doses where solicited symptoms are indicated as being absent/present in case more than 5% of the doses are not documented.

AE relationship to vaccination is defined as the relationship to at least one study vaccine as identified by the investigator. In case the related vaccine has not been specified the adverse event will be considered related to all study vaccines. The percentage of subjects reporting of causally related solicited symptoms and unsolicited adverse events within the 31-day (Days 1-31) post-vaccination period will be provided by group for each study vaccine separately.

The planned analysis of the percentage of doses and of subjects reporting at least one grade 3 causally related symptom (solicited or unsolicited) during the 8 day (Day 1-Day 8) solicited follow-up period post-vaccination will not be generated considering this analysis is of limited clinical relevance and is not part of the standard analyses planned in other PCV free Rota studies.

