11. ANNEX 1 STANDARD DATA DERIVATION RULE AND STATISTICAL METHODS

11.1. Statistical Method References

The exact two-sided 95% CIs for a proportion within a group will be the Clopper-Pearson exact CI [Clopper CJ, Pearson ES. The use of confidence or fiducial limits illustrated in the case of binomial. *Biometrika*. 1934;26:404-413].

The standardised asymptotic two-sided 95% CI for the group difference in proportions is based on the method described in the following paper: Robert G. Newcombe, interval estimation for the difference between independent proportions: comparison of eleven methods, *Statist Med*. 1998; 17, 873-890]. The standardised asymptotic method used is the method six.

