11.2.2. Dose number

- The study dose number is defined in reference to the number of study visits at which vaccination occurred. More specifically dose 1 refers to all vaccines administered at the first vaccination visit while dose 2 corresponds to all vaccinations administered at the second vaccination visit even if this is the first time a product is administered to the subject.
- Relative dose: the relative dose for an event (AE, medication, vaccination) is the most recent study dose given before an event. In case the event takes place on the day a study dose is given, the related dose will be that of the study dose, even if the event actually took place before vaccination. For instance, if an adverse event begins on the day of the study vaccination but prior to administration of the vaccine, it will be assigned to this dose. In case a study dose is not administered and an event occurs after the subsequent study dose (eg 3rd study dose), the relative dose of the event will be study dose associated to the subsequent study dose (eg dose 3).
- The number of doses for a product is the number of time the product was administered to a subject.
- The incidence per dose is the number of vaccination visits at which an event was reported among all vaccination visits.

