	HRV LYO	299	247	82.6	77.8	86.7
Overall/dose	HRV LIQ	595	498	83.7	80.5	86.6
	HRV LIQ	603	527	87.4	84.5	89.9
	HRV LIQ	600	483	80.5	77.1	83.6
	LIQPOOL	1798	1508	83.9	82.1	85.5
	HRV LYO	599	496	82.8	79.5	85.7
Overall/subject	HRV LIQ	298	283	95.0	91.8	97.2
	HRV LIQ	302	287	95.0	91.9	97.2
	HRV LIQ	300	275	91.7	87.9	94.5
	LIQPOOL	900	845	93.9	92.1	95.4
	HRV LYO	300	279	93.0	89.5	95.6

HRV LIQ = HRV vaccine liquid formulation Lot A HRV LIQ = HRV vaccine liquid formulation Lot B

HRV LIQ = HRV vaccine liquid formulation Lot C LIQPOOL = Pooled HRV vaccine liquid formulation

HRV LYO = HRV vaccine HRV Lyophilised formulation

For each dose:

N = number of subjects having received the considered dose

n/% = number/percentage of subjects reporting at least one symptom for the considered dose

For overall/dose:

N = number of administered doses

n/% = number/percentage of doses followed by at least one symptom

For overall/subject:

N = number of subjects with at least one administered dose

n/% = number/percentage of subjects reporting at least one symptom

95% CI = exact 95% Confidence Interval, LL = Lower Limit, UL = Upper Limit

Template 19 Percentage of doses with solicited general symptom including those rated grade 3 in intensity and those assessed as related to vaccination during the 8-day (Day 1 to Day 8) follow-up period, for each dose in the pooled HRV vaccine liquid formulation group and the HRV vaccine HRV Lyophilised formulation group - Exposed Set

		LIQPOOL					HRV LYO				
					95 % CI					95 % CI	
Symptom	Type	N	n	%	LL	UL	N	n	%	LL	UL
Dose 1											
Cough/runny nose	All	900	233	25.9	23.1	28.9	300	79	26.3	21.4	31.7
	Grade 3	900	2	0.2	0.0	0.8	300	4	1.3	0.4	3.4
	Related	900	187	20.8	18.2	23.6	300	64	21.3	16.8	26.4
Diarrhoea	All	900	25	2.8	1.8	4.1	300	4	1.3	0.4	3.4
	Grade 3	900	7	0.8	0.3	1.6	300	1	0.3	0.0	1.8
	Related	900	25	2.8	1.8	4.1	300	3	1.0	0.2	2.9
Fever(°C)	All	900	179	19.9	17.3	22.6	300	68	22.7	18.1	27.8
	Grade 3	900	2	0.2	0.0	0.8	300	0	0.0	0.0	1.2
	Related	900	174	19.3	16.8	22.1	300	67	22.3	17.7	27.5
Irritability	All	900	629	69.9	66.8	72.9	300	207	69.0	63.4	74.2
	Grade 3	900	38	4.2	3.0	5.7	300	12	4.0	2.1	6.9
	Related	900	607	67.4	64.3	70.5	300	201	67.0	61.4	72.3
Loss of appetite	All	900	231	25.7	22.8	28.7	300	67	22.3	17.7	27.5
	Grade 3	900	1	0.1	0.0	0.6	300	1	0.3	0.0	1.8
	Related	900	220	24.4	21.7	27.4	300	63	21.0	16.5	26.1
Vomiting	All	900	136	15.1	12.8	17.6	300	55	18.3	14.1	23.2
	Grade 3	900	25	2.8	1.8	4.1	300	11	3.7	1.8	6.5

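### Overall/dose safety percentages get an exact 95% CI that treats an infant's two HRV doses as independent, so the interval is too narrow for common symptoms if doses within an infant are positively correlated

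*SAP*

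**What the plan says.** SAP 6.4.1, which repeats Protocol 10.8, plans dose-level and subject-level percentages with exact 95% intervals. This applies to any symptom ("The percentage of doses and of subjects reporting at least one symptom (solicited or unsolicited") and to individual symptoms ("The percentage of doses and of subjects reporting each individual solicited general symptom will be computed").

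The interval is fixed in SAP 11.1: "The exact two-sided 95% CIs for a proportion within a group will be the Clopper-Pearson exact CI". SAP 6.3.1.3 names the same method.

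The unit of analysis is the dose. SAP 6.4.2 says "Safety analysis will be done per administered dose", and SAP 11.2.2 says "The incidence per dose is the number of vaccination visits at which an event was reported among all vaccination visits". In the mock tables of SAP Annex 3, the overall/dose footnote to Template 18 reads "N = number of administered doses" for the denominator and "n/% = number/percentage of doses followed by at least one symptom" for the numerator.

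Each infant receives two HRV doses (SAP section 2). Neither document mentions repeated doses in the same infant when describing these intervals.

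**The concern.** Clopper-Pearson is exact for a count of independent trials. An overall/dose row pools Dose 1 and Dose 2, so every infant who receives both doses enters twice. An infant who is irritable or feverish after the first dose may well be more likely than average to be so after the second. If so, 1280 doses carry less information than 1280 independent trials, and the printed interval is too short.

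The study report would then show an interval labelled exact 95% that overstates how precisely a common symptom's per-dose rate is known. Nothing else is at stake. Dose 1, Dose 2 and overall/subject rows use one observation per infant and are not affected.

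**Working it through.** **Inputs.** There are 640 infants per group (SAP Table 1) and two HRV doses per infant, so up to 1280 doses per group. The interval is two-sided 95% Clopper-Pearson. The within-infant correlation rho is not in the documents; 0.10 to 0.31 is assumed.

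**1. Reproduce the mock intervals.** In Template 18 each overall/dose count is the sum of the two dose rows; for Lot A, 251 + 247 = 498 and 298 + 297 = 595. The limits are LL = Beta(0.025; x, n−x+1) and UL = Beta(0.975; x+1, n−x). All five printed intervals come back to one decimal:

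| Row | x/n | Plain Clopper-Pearson |
|---|---|---|
| Lot A | 498/595 | 80.5-86.6 |
| Lot B | 527/603 | 84.5-89.9 |
| Lot C | 483/600 | 77.1-83.6 |
| Pooled liquid | 1508/1798 | 82.1-85.5 |
| Lyophilised | 496/599 | 79.5-85.7 |

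The layout therefore does treat pooled doses as independent.

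**2. What correlation is plausible?** Template 18 holds placeholder counts from a three-lot study, so this step only illustrates. The proportion with a symptom after both doses is p12 = p1 + p2 − p_any, and rho = (p12 − p1·p2)/√(p1·q1·p2·q2), where q = 1 − p.

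- Lot A: p1 = 251/298 = 0.842, p2 = 247/297 = 0.832, p_any = 283/298 = 0.950.
- p12 = 0.724 and p1·p2 = 0.700, so rho = (0.7243 − 0.7005)/0.1364 = 0.174.
- The other rows give 0.309 (Lot B), 0.292 (Lot C), 0.261 (pooled) and 0.284 (lyophilised).

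With two doses per infant the design effect is 1 + rho. Standard errors are thus understated by a factor of √1.174 = 1.08 to √1.309 = 1.14. Using effective n = n/(1 + rho), Lot A becomes 80.2-86.8 and the lyophilised row 79.1-86.1.

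**3. True coverage at this trial's size.** For 640 pairs with P(both) = p² + rho·p·q and P(neither) = q² + rho·p·q, the exact distribution of the total count out of 1280 gives the coverage of the planned interval:

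| True rate | rho 0 | 0.10 | 0.17 | 0.31 |
|---|---|---|---|---|
| 83% | 95.1% | 94.0% | 93.2% | 91.5% |
| 25% | 95.5% | 94.4% | 93.6% | 92.0% |
| 3% | 96.0% | 94.9% | 94.2% | 92.7% |
| 1% | 96.7% | 95.8% | 95.2% | 93.8% |

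Coverage at rho 0 is at least 95% throughout, so the shortfall comes from the correlation alone. At a 1% rate and rho 0.20, coverage is still 94.9%.

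**4. Shift in the limits at 1280 doses, using effective n.**

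| Rate | Planned | rho 0.10 | rho 0.17 | rho 0.31 |
|---|---|---|---|---|
| 83% (1062/1280) | 80.8-85.0 | 80.7-85.1 | 80.6-85.2 | 80.5-85.3 |
| 25% (320/1280) | 22.7-27.5 | 22.5-27.6 | 22.5-27.7 | 22.3-27.8 |

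The intervals widen by about 5%, 8% and 15%.

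**The case against.** The strongest reply is that this is immaterial. SAP section 7 makes all safety output descriptive, no between-group safety test is planned, and the after-each-dose endpoint is answered by the Dose 1 and Dose 2 rows, which are valid. At rho 0.10 each limit moves by about 0.1 point, the last printed digit. At rho 0.05 coverage is 94.6% at an 83% rate, and nothing in the documents rules that value out. The 0.17-0.31 values come from another study's placeholder counts for one composite endpoint; carrying them to 25%, 3% or 1% events is extrapolation. All of this stands, and it is why the point is minor. It does not make the 95% label correct.

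A second reply concerns the unit. SAP 11.2.2 and the denominator table in SAP 11.2.5 refer to all vaccination visits, of which there are three, so two doses per infant is an interpretation. It is the better one: solicited symptoms are collected only after the two HRV doses, and Template 18 pools exactly two. For an event collected after all three visits the design effect would be 1 + 2·rho, which worsens the undercoverage.

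A third reply is that pooling is unclear for individual symptoms, because Template 19 gives separate dose rows and the overall/dose block of Template 20 merely repeats the Dose 1 figures. That is fair about the mock-ups. The SAP text still plans a percentage of doses for each symptom, and Templates 22 and 25 also carry dose-based denominators (603 and 600) with 95% intervals.

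**Conclusion.** The concern holds, at low weight. As written, the overall/dose intervals assume independence between two doses in one infant, and the documents neither justify nor caveat this. If rho lies between 0.10 and 0.31, nominal 95% intervals for common symptoms cover about 91.5 to 94.4%, and each limit is too close to the estimate by about 0.1 to 0.4 percentage point. If rho is near zero, or the event is near 1% with rho no more than about 0.2, there is no practical error.

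The mechanism is certain and its direction is certain given positive correlation. The size rests on an assumed rho, since this trial's value is unknown until data are available. No confirmatory result, and no row that counts each infant once, is affected.

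**What to change.** Keep Clopper-Pearson for Dose 1, Dose 2 and overall/subject rows. For overall/dose rows, state one of these in the SAP:

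- **Drop the interval.** Print the overall/dose percentage without a CI. This is the simplest option and loses nothing for the stated endpoints.
- **Effective sample size.** Apply Clopper-Pearson with n/(1 + rho), estimating rho from the two doses and setting it to 0 if negative. If fewer than 10 doses have the event, or fewer than 10 lack it (including zero-event rows, where rho cannot be estimated), use plain Clopper-Pearson and footnote it. In simulation at 640 infants, with rates of 83, 25, 14, 3 and 1% and rho from 0 to 0.31, coverage was 95.2-96.8% in every cell.
- **GEE with robust variance**, the infant as cluster, and the same fallback for sparse rows. This also handles a row that pools more than two visits, where the factor 1 + rho would no longer be right.

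The SAP should also say which visits form the overall/dose denominator.

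The cost is a sentence in the SAP, a table footnote and a small programming change. At rho 0.17 to 0.31 the affected intervals become about 8-15% wider; at an 83% rate, total width goes from 4.2 to 4.5-4.8 points. Data collection and sample size do not change.
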